The intervention will be divided into three steps. At Step 1 for 3 months, the treatment arm will receive electronic monitoring (of participants' BP, weight, physical activity, food diary, and medication-taking) with weekly Interactive Technology Enhanced Coaching (ITEC) while the control arm will receive usual care with manual BP measurements monthly. At Step 2 for three months, the treatment arm will receive electronic monitoring with ITEC biweekly, and the control arm will receive electronic monitoring only. At Step 3 for three months, both the treatment arm and the control arm will receive electronic monitoring only.

Information from this study may be used to enhance self-care management, control blood pressure, and increase the quality of life for Black women who are burdened with the adverse effects of HTN and its high disability and mortality rates.

Our sample of n=45 participants per arm (N=90 in total), will be measured (electronic measurements, anthropometric measurements, and data collection tools) at baseline, 3 months, 6

months, and at 9 months post CDSMP. A hierarchical, mixed-effects repeated measures design will be used to analyze the data.

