## Technology

After completing the CDSMP sessions, study participants were randomly assigned to either the treatment (ITEC) or the control arm (IT).

The technology component of the study was linked to Fitbit Plus, a cloud-based collaborative care platform that was designed to store and track data. The PI was trained in the Fitbit Plus platform, synchronizing data collection devices, instructing participants in the use of equipment, monitoring participant data, and interactive coaching messages. In the privacy of their homes, or another preferred location, each study participant received individualized instruction (about 45 to 90 minutes) to Fitbit Plus and all study tools accommodating various technological skills.

Study equipment included three wireless tools (Omron BP monitor, Fitbit activity tracker, and Fitbit weight scale) and five apps (Omron Connect, Fitbit, MyFitnessPal, Apple Health if iPhone user or Google Fit if android user, and Fitbit Plus). Apps were installed and tools synchronized to the participant’s smartphone. Apple Health and Google Fit allowed Fitbit Plus to import app data from Fitbit, MyFitnessPal, and Omron. Participant action plans were set up in Fitbit Plus to correspond to the study aims. As participants wore their Fitbit activity tracker, took their BP, stepped onto the weight scale, or entered food intake, their measurement data were transmitted in real time via Wi-Fi and Bluetooth Smart technology to the Fitbit Plus dashboard. In the dashboard, participants could view their data along with the PI. Two exceptions were the manual BP recording for Android users and the manual self-reported medication-taking for all participants, as described under Fitbit Plus Measures. The PI monitored all study participant data during a two-week trial period to allow participants an opportunity to adapt to using the wireless tools and apps. Once the orientation period was over, data were monitored via the Fitbit Plus platform for study purposes.

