**Physical Activity tracker.** Fitbit Inspire HR (Diaz et al., 2015; *Fitbit Inspire and Inspire HR*, 2019) is a physical activity tracker and accelerometer that measures steps, distance, calories burned, and active minutes. The Fitbit was worn on the non-dominant wrist to monitor physical activity during waking hours. Steps in the Fitbit app were synchronized to the Fitbit Plus dashboard. The outcome of interest for this study was changes in the number of steps.

**MyFitnessPal Food Diary.** MyFitnessPal app is used with smartphones to log food intake using a comprehensive food database (Van Horn et al., 2016). MyFitnessPal calculates calories, macronutrients (such as carbohydrates, fats, proteins), and micronutrients (such as vitamins, and minerals) from the food intake. Caloric and sodium intake were synchronized to the Fitbit Plus dashboard. Because sodium is known to increase BP, it was monitored to provide insight to the participant's dietary patterns. Participants were instructed to log their food intake immediately after eating. The outcome of interest in this study was changes in caloric intake.

**Weight Scale.** The Fitbit Aria 2 weight scale (Wi-Fi Smart Scale) was used to measure weight, BMI, and body fat percentage. Participants were instructed to weigh every morning after emptying their bladder. Weight measurements were synchronized via the Fitbit app to the Fitbit Plus dashboard. This study examined changes in body weight.

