## Fitbit Monitoring

With smart monitoring of connected devices in Fitbit Plus, data were tracked, analyzed, and transparently displayed to provide opportunities for participants to better understand their condition and self-manage by being actively engaged in their own care. In the CDSMP, all participants were taught to write action plans and report if they were successful, partially successful, or not successful in achieving their plan based on participant self-tracking of their data. Fitbit Plus allowed real-time adherence tracking. If participants were adhering to their action plan, study measures displayed a green color indicating a positive trend and if they were not adhering, measures would display a red color indicating a negative trend, alerting the PI to communicate with participants and encourage active engagement in their self-care.

Only the treatment arm action plans were monitored with individualized coaching messages (ITEC) via secure text messaging in the Fitbit Plus dashboard with real-time participant feedback. Coaching messages focused on helping participant's problem-solve barriers to goal

achievement with relevant dialogue to encourage BP control, medication adherence, and lifestyle modifications (physical activity, caloric intake, and weight management). The PI sent tailored ITEC messages via Fitbit Plus to treatment arm participants weekly for months 1-3, biweekly for months 4-6, and no ITEC messages for months 7-9 (to assess for sustainability).

During months 1-3, the control arm received usual care only, along with monthly manual BP and weight measures. After that time, the control arm was given the same wireless tools and apps as the treatment arm. In addition, they received individualized instruction equivalent to the treatment arm and practiced using the tools during a two-week trial period. For months 4-9, the control arm was monitored with IT via Fitbit Plus with no coaching. Fitbit Plus was used only to track participants for comparative data with the treatment arm. The control participants were not contacted between data collection periods, except to send reminders if they were not participating in daily measures.

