All baseline manual measurements and study questionnaires were repeated at 3, 6, and 9 months. All other data were collected through the Fitbit Plus Platform via wireless tools. Personal contact every three months for about 30 minutes provided a human element to the Fitbit Plus technology component and allowed the PI to troubleshoot any problem areas or equipment issues.

Gift cards were given to participants for time expended for baseline assessment (\$20) and repeated measures at 3- (\$30), 6- (\$40), and 9-months (\$60) totaling \$150.

If study participants completed all parts of the research study, then as a completion bonus, they were allowed to keep all measurement tools including the blood pressure monitor, Fitbit, and weight scale, along with the CDSMP book at the conclusion of the study. After Fitbit Plus access ended, participants were able to continue to monitor themselves through the corresponding apps on their smartphone. For those study participants who do not complete the study, the blood pressure monitor, Fitbit, weight scale, and book were returned to the PI when they exited the study.

At the completion of the study, Fitbit Plus transmitted a copy of all collected data at the request of the PI. Both the PI and study participants instructed Fitbit Plus to delete all study participant data when the study ended.

A summary of the overall results of the project in ‘lay’ language was shared with participants in their preferred format (such as email, letter, or in-person) while ensuring confidentiality of individual responses after the study has ended.

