### Statistical Analysis Plan

**Sample size and power.** All participants meeting study eligibility requirements received the CDSMP classes for 6 weeks. Participants from this pool were randomized to the treatment arm (with ITEC and electronic devices such as the home BP monitoring, weight scale, and physical activity tracker), and the control arm, with IT monitoring only. Our sample of  $n=45$  participants per arm ( $N=90$  in total), measured at baseline, and at 3-, 6-, and 9-months post CDSMP, has approximately 80% power (assuming 5 dropouts per arm) to detect an effect size of  $\sim 0.205$  or greater at the  $\alpha=0.05$  level of statistical significance, given a realistic range of simulated unstructured covariance matrices. Assuming an 11% rate of attrition, the enrollment target was set at 90 for both arms, which would yield a final sample of 80 participants, or 40 per arm.

**Statistical analysis.** A hierarchical, mixed-effects repeated measures design was used to analyze the primary and secondary outcomes of interest. This model, which allows for heterogeneous variances across time points, is preferred over a simple univariate model that requires compound symmetry (i.e., the correlation between a measurement at time  $T_i$  and any other measurement within the same patients at  $T_j$ , is equal for all  $i$  and  $j$ ). A mixed-effects model is more efficient for handling missing at random (MAR) data than, for example, a generalized estimating equations (GEE) repeated measures approach, which requires the more restrictive assumption that missing data are missing completely at random (MCAR). We performed a sensitivity analysis using both a GEE model and sequential application of the EM algorithm to impute missing data. Data from participants ( $n=7$ ) who dropped out of the study before their first post-CDSMP visit were not included in the analysis. However, baseline information for these participants were compared with participants who continued in the study.

When appropriate a constrained longitudinal data analysis (cLDA) model was used, assuming the same baseline mean for treatment and referent arms with missing baseline data. The cLDA model examines treatment differences over time. Coffman et al. (2016) cite the cLDA as the method of choice for longitudinal RCTs because it yields robust estimates of treatment effect differences under reasonable missing data assumptions.

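### Steps, caloric intake and Fitbit Plus medication adherence have no baseline and no month-3 control data, yet the plan schedules electronic measurement at all four times and makes no exception for these outcomes

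*Combined protocol and SAP*

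**What the plan says.** Description of the Study says that 45 participants per arm "will be measured (electronic measurements, anthropometric measurements, and data collection tools) at baseline, 3 months", and then at 6 and 9 months. The Statistical Analysis Plan, under sample size and power, uses the same four times: "measured at baseline, and at 3-, 6-, and 9-months post CDSMP, has approximately 80% power", with 40 per arm remaining after dropout. It describes the control arm as having IT monitoring only. One mixed-effects repeated-measures model serves the primary and secondary outcomes. A constrained longitudinal (cLDA) model with a common baseline mean is used when appropriate, and GEE and EM imputation are sensitivity analyses.

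Fitbit Monitoring describes the control arm differently: "During months 1-3, the control arm received usual care only, along with monthly manual BP and weight measures". It continues: "After that time, the control arm was given the same wireless tools and apps as the treatment arm". Controls then had a two-week practice period and were monitored through Fitbit Plus in months 4-9. The same section repeats the manual measurements and questionnaires at 3, 6 and 9 months and adds: "All other data were collected through the Fitbit Plus Platform via wireless tools".

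Fitbit Plus Technology Measures defines the device outcomes as changes. For activity: "The outcome of interest for this study was changes in the number of steps". For diet: "The outcome of interest in this study was changes in caloric intake". Medication adherence from the Fitbit Plus self-report is likewise examined as change in average adherence.

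**The concern.** The scheduled electronic measurements cannot all exist. Three outcomes under aim 2 come only from the devices and apps, and for them the baseline and the month-3 arm comparison are missing by design. A model that assumes four times in both arms would have to extrapolate or impute cells in which nobody was measured. The alternative, using each arm's first device reading as its baseline, would compare a treatment-arm change that starts at about month 0 with a control-arm change that starts at about month 3. Readers could not tell which period a reported change in steps covers. They might also credit a null result on steps or calories with 80% power that was worked out for a fuller schedule.

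**Working it through.** **1. Which cells can hold data.**
- Baseline data lists demographics, manual measurements and questionnaires. The CDSMP section places this collection before the six-week programme.
- Technology describes randomisation after the programme, and device set-up only after that. That the treatment arm had no devices at baseline is inferred from this order. For controls the timing is explicit in Fitbit Monitoring, and Step 1 in Description of the Study agrees.
- No manual or questionnaire measure of steps or calories is described. The Hill-Bone scale covers adherence at all four visits but is a different measure from the Fitbit Plus self-report.

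| Device outcome | Baseline | Month 3 | Month 6 | Month 9 |
|---|---|---|---|---|
| Treatment | none | data | data | data |
| Control | none | none | data | data |

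Five of eight cells can be filled.

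**2. What can be estimated.** With a separate mean for each filled cell (T3, T6, T9, C6, C9):
- Estimable: T6−C6, T9−C9, their average, and (T9−T6)−(C9−C6).
- Not estimable: the arm difference at baseline or month 3, the arm difference averaged over months 3, 6 and 9, and any change from baseline in either arm.
- A common baseline mean (cLDA) does not help, because no baseline value exists from which to estimate it.

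**3. The plan's own figures.** Attrition reproduces: 5/45 = 11.1%, and 80/(1−0.11) = 89.9, or 90. The 80% can be neither confirmed nor refuted, because the contrast, the effect-size scale and the covariance matrices are not given. If 0.205 is a standardised mean difference, one visit with 40 per arm gives 15% (two-sided), and a baseline-adjusted mean of three visits reaches 80% only at a correlation of about 0.91. If it is Cohen's f (difference 2 × 0.205 = 0.41 SD), the latter analysis gives about 78% to 81% at correlations of 0.2 to 0.5. So about 80% is attainable on some readings.

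**4. Illustration of what the empty cells cost.** Assumptions, not in the documents: two-sided 0.05, equal correlation r between visits, and equal effect and SD at each visit. From the SAP: n = 40 per arm. Variance factors for the arm mean, in units of SD²:
- four-time design, baseline-adjusted mean of months 3, 6 and 9: v₁ = (1+2r)/3 − r² (77 df)
- months 6 and 9 only, no baseline: v₂ = (1+r)/2 (78 df)

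Power comes from the noncentral t with noncentrality d/√(2v/n). For each r, d is set to give 80% with v₁ and is then used with v₂. The detectable-effect ratio is √(v₂/v₁).

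Example, r = 0.5: v₁ = 2/3 − 0.25 = 0.417 and d = 0.410; v₂ = 0.75. Noncentrality = 0.410/√(2×0.75/40) = 2.12, power 55%. Ratio = √(0.75/0.417) = 1.34.

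| r | v₁ | v₂ | d with 80% power | Power, months 6 and 9 | Detectable-effect ratio |
|---|---|---|---|---|---|
| 0.2 | 0.427 | 0.60 | 0.414 | 66% | 1.19 |
| 0.3 | 0.443 | 0.65 | 0.422 | 64% | 1.21 |
| 0.4 | 0.440 | 0.70 | 0.421 | 60% | 1.26 |
| 0.5 | 0.417 | 0.75 | 0.410 | 55% | 1.34 |
| 0.6 | 0.373 | 0.80 | 0.388 | 48% | 1.46 |
| 0.7 | 0.310 | 0.85 | 0.353 | 39% | 1.66 |

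This comparison does not depend on the scale of 0.205.

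**The case against.** The staggered design is disclosed: Step 1 and Fitbit Monitoring both say that controls had manual measurements only in the first three months. The schedule conflict therefore comes down to one parenthesis in Description of the Study. The SAP's power sentence says only that participants were measured, which is true of manual BP, weight and the questionnaires. It names no outcome and claims no power for steps or calories. All of this stands, so the power sentence is not itself false.

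A reader might infer that aim 1 has the same gap, because change in BP is mentioned under the wireless monitor and manual BP is said to verify it. The documents do not support that. The SAP's paired tests of BP and weight/BMI run from baseline to month 3 in the referent group too, and for controls only manual readings can supply them.

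It can also be said that a change need not be a change from baseline, that cLDA is used only when appropriate, and that arm differences at months 6 and 9 are estimable. These points are correct, but the plan does not say which contrast applies to the device outcomes, and it exempts none of them from the common model or from EM imputation. The missing-at-random discussion does not mention cells that are empty by design.

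The two-week practice period is not a usable baseline. It follows randomisation, it falls about three months later in controls, and Technology says that monitoring for study purposes began after it.

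**Conclusion.** The point holds for steps, caloric intake and Fitbit Plus medication adherence: 5 of 8 cells, no baseline and no month-3 arm comparison. It rests on the documents' own timeline, explicit for controls and inferred for the treatment arm before randomisation. Manual BP, weight/BMI, waist circumference and questionnaires are complete by design. Aim 1 is unaffected provided manual BP is the analysed BP.

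A reader might also take the table as proof that the stated 80% is wrong. It is not: the contrast and the correlations are assumed. It shows only that an effect with 80% power under four-time measurement would have less power for these outcomes, about 66% to 39% over the assumed range. This should be fixed. It concerns device outcomes under aim 2, not the BP result.

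**What to change.** 1. **Description of the Study.** State that manual BP, weight, waist circumference and questionnaires are measured in both arms at baseline, 3, 6 and 9 months, and that electronic measures exist from month 1 in the treatment arm and from month 4 in the control arm, with no electronic baseline.
2. **SAP, sample size and power.** Describe the control arm as usual care in months 1-3 and IT monitoring in months 4-9. Limit the power statement to outcomes measured in both arms at all four times. State that BP is analysed from the manual readings.
3. **SAP, statistical analysis.** Add a paragraph: steps, caloric intake and Fitbit Plus medication adherence are compared between arms as means over months 4-6 (excluding the control arm's two-week trial period) and, separately, over months 7-9, with 95% confidence intervals and no baseline adjustment. Change from baseline, a month-3 comparison and imputation of the cells empty by design are not used, and 80% power is not claimed.

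The cost is a few sentences and one paragraph, with no change to enrolment, data collection or the sponsor's simulation. Two limits should be stated with it. The arms differ in prior device exposure, most of all in months 4-6. And because the SAP is written in the past tense and already reports 7 early dropouts, the change should be labelled as a correction and not presented as prespecified.

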Both models are valid for repeated measures if data are missing at random (MAR). Little's test was used to determine if variables were missing completely at random (MCAR) while significant covariate-dependent missing values were identified by regressing a dichotomous indicator variable for missingness against key models factors. (Li, 2013) That is, if the missing values were non-randomly associated with the latter variables of interest, the mechanism was deemed to be missing at random (MAR). A sampling of observed vs. non-unobserved items were subjectively scrutinized for signs of a 'missing not at random (MNAR)' pattern for the data. Overall, no relevant violation of the MAR assumption was evident in our analyses.

Descriptive statistics were used to summarize demographic data (such as marital status, education, and income) of study participants.

An independent (unpaired) samples t-test was used to determine the difference between the means of the treatment and referent groups. The dependent (paired) sample t-test was used to determine the mean differences between variables (systolic and diastolic BP and weight/BMI) for treatment and referent group participants from baseline (post-CDSMP) to month 3, from month 3 to 6, and from month 6 to 9. Time frames were allotted to further participant engagement in self-management.

The use of a two-sample t-test versus non-parametric methods for nonnormally distributed data has been debated in the literature (le Cessie et al., 2020). In general, the former is reasonable robust to departures from normality, providing that the sample sizes are sufficiently large, and the underlying variances are finite (with no extreme outliers) (Lumley et al., 2002)

All data collection tools (except the Hill-Bone CHBPTS medication subscale) were converted to a 100-point scale to enable comparison. Questionnaire scores were analyzed for changes across several time points using a mixed-effects repeated measures model for both groups. In comparison to a repeated measures ANOVA test, the mixed model tends to yield valid estimates of treatment effects even when the missing values are not completely missing at random (Detry & Ma, 2016). Rounding was based upon significant digits rather than a fixed number of decimal places (i.e., Goldilocks method) (Efird, 2021). Data were analyzed using SAS - v 9.4 (Cary, NC).

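### The EM sensitivity analysis reads as single imputation with no carried uncertainty, so its standard errors are modestly too small or its effect modestly shrunken

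*Combined protocol and SAP*

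**What the plan says.** In the Statistical Analysis Plan, under Statistical analysis, the main method is a likelihood-based model: "A hierarchical, mixed-effects repeated measures design was used to analyze the primary and secondary outcomes of interest". A constrained longitudinal model (cLDA) is used where appropriate, and the SAP relies on MAR for both.

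The check on missing data is one sentence, which pairs GEE with "sequential application of the EM algorithm to impute missing data". The next sentence excludes 7 participants who left before their first visit after the CDSMP. The SAP does not define what is sequential about the EM step. It also does not give the variables in the EM model, the number of filled data sets, the model fitted to them, or how their standard errors were obtained.

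Of the companion method, GEE, the SAP says that it is one "which requires the more restrictive assumption that missing data are missing completely at random (MCAR"). The mechanism of missingness was examined with Little's test and by "regressing a dichotomous indicator variable for missingness against key models factors".

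Under Sample size and power, the plan allows for 5 dropouts per arm: "Assuming an 11% rate of attrition, the enrollment target was set at 90 for both arms". It expects 80 women to finish, 40 in each arm. No missing rate by visit or arm is given.

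**The concern.** EM is a way to maximise a likelihood. Used to fill gaps, it returns one fitted value per gap, with no residual scatter and no allowance for the estimation of the imputation model. If the filled data set is then analysed as though complete, two errors are possible, depending on a detail that the SAP omits.

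- **Arm in the EM model.** The estimate is sound, but women who left count as observed and lie exactly on the fitted surface. The residual variance and the standard error are too small.
- **Arm left out.** Missing values in both arms are filled toward a common mean, and the difference between arms shrinks.

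Readers will take agreement between this analysis and the main model as robustness. If its p-values are somewhat too small or its effect somewhat attenuated, both agreement and disagreement are harder to interpret.

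**Working it through.** **Inputs from the SAP.** 90 enrolled, 45 per arm; 11% attrition, or 5 dropouts per arm; 80 at the end; visits at baseline and months 3, 6 and 9; 7 early dropouts excluded.

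**Assumed, because not given.** Compound-symmetric correlation 0.4–0.6, SD 15 mmHg, monotone dropout, two-sided 5% test, baseline-adjusted comparison at month 9, and an illustrative true effect of −8 mmHg for the attenuation.

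**The plan's own figure.** 90 × (1 − 0.11) = 80.1, and 10/90 = 11.1%. Both agree with the stated 80.

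**Who could be imputed.** If 90 were enrolled, 90 − 7 = 83 are analysed, about 41 per arm. Two cases:
- *Low:* total dropout is the planned 10 and 7 of these are the excluded women. Then 3 of 83 have filled values, m = 3.6%.
- *Higher:* a further 5 per arm of about 41 leave after month 3. Then m = 10/82 = 12.2%.

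**Approximation, arm in the model.** Let n be the number per arm, m the fraction filled and σ² the residual variance. Suppose the filled points add no residual and no information.
- True variance of the difference ≈ 2σ² / [n(1 − m)].
- Reported variance ≈ 2σ²(1 − m) / n, since the residual sum of squares comes from n(1 − m) women per arm but is divided by about n.
- Reported SE / true SE ≈ 1 − m, and type I error ≈ 2[1 − Φ(1.96(1 − m))].

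| Case | m | SE too small by | 1.96(1 − m) | Type I error |
|---|---|---|---|---|
| 3 of 83 | 3.6% | 3.6% | 1.889 | 5.9% |
| 5 per arm of 41 | 12.2% | 12.2% | 1.721 | 8.5% |

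**Simulation, arm in the model.** This fills from all earlier visits, as EM would.

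| Case | Month-9 SE too small by | Month-9 type I error |
|---|---|---|
| 3 of 83 | about 3–5% | about 5.5–6% |
| 5 per arm of 41, after month 3 | about 10–12% | about 7.5–9% |

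Monte Carlo error near 5% with 6,000 runs is √(0.05 × 0.95 / 6000) = 0.3 percentage points. For the baseline-adjusted mean of months 3–9, type I error is about 5–6%.

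**Check that the imputation is the cause.** Complete-case analysis at 11–12% missing gave type I error of 4.4–5.0%. A separate simulation at correlation 0.5, with dropout depending on the month-3 value, gave the same picture. With arm-specific EM, the reported SE was 1–4% too small at 3.6% missing and 8–13% too small at 11%.

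**Arm left out.** If the filled values carry none of the effect, the estimate is δ(1 − m). With δ = −8 mmHg this is −8 × 0.964 = −7.7 or −8 × 0.878 = −7.0. Months 3 and 6 carry part of the effect into the filled values, so the simulated loss is smaller: about −7.4 to −7.5 for 5 per arm of 41. Type I error then stays near 5%.

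**The case against.** **The SAP does not say that values were filled once and analysed as observed.** This is correct. A reader might take single filling as a stated fact, but it is only the natural reading of a sentence that says nothing about draws or variance. If something else was done, the SAP should say so; the sentence needs changing either way.

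**The planned 11% overstates the problem.** Largely right. Imputing 5 of 45 per arm with dropout in all three intervals gives type I error of about 8%. That includes women lost before month 3, who carry the most filled values. If the first post-CDSMP visit is month 3, they are excluded and never imputed. Attrition well above 11% has no basis in the documents. The low case may still be a floor. The SAP anticipates missing baseline data, and under Fitbit Monitoring the control arm had no devices in months 1–3. Whether EM was applied to device outcomes is not stated.

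**Month 9 alone is an unfavourable choice of test.** This stands. The SAP names a repeated-measures model over all visits, and a test on the mean over visits is affected less.

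**The sensitivity analysis also includes a GEE.** This stands too. A GEE on observed data does not have this standard-error flaw. A reader might infer from the MCAR remark that the GEE is invalid or must be weighted. The SAP discloses the stricter assumption openly and does not report that missingness depended on covariates. Inverse-probability weights fitted to so few dropouts could be unstable, so no weighting is asked for.

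**Multiple imputation rests on the same MAR assumption as the main model.** True. It would correct the error bars and would not test departures from MAR, which is a separate question.

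**Conclusion.** The point holds in limited form. As written, the EM step has nothing that carries imputation uncertainty into the standard errors, and its result leans one of two ways depending on an unstated choice about arm. On the assumptions above, the month-9 standard error is too small by about 3–5% in the low case and 10–12% in the higher case. With arm omitted, the effect would be attenuated instead. The documents do not show which case applies, because they give no missing rate after the exclusion.

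A reader might infer that the trial's main result is in doubt. The documents do not support this: the mixed model and cLDA use the observed data, and no primary estimate or sample size depends on the EM step. Nor does it follow that the sensitivity analysis as a whole is worthless, since the GEE is a separate analysis. What is weakened is the EM result as evidence of robustness. Severity is minor to moderate; confidence is moderate, because single filling is inferred.

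**What to change.** 1. Replace the EM fill by multiple imputation: for example 50 data sets, with arm and all visits in the imputation model, each analysed with the main model and combined by Rubin's rules. PROC MI and PROC MIANALYZE in the SAS 9.4 already named will do this.
2. Because the SAP is written in the past tense, state what the EM step did: variables in the model, whether arm was included, number of filled data sets, analysis model and variance method.
3. Report missing values by arm, visit and outcome among the women analysed, so that readers can judge the size.

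The cost is a few lines of code, a sentence or two in the SAP and a slightly wider sensitivity interval. The main analysis and the GEE need no change for this point.
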